The main outcome of this analysis was defined a-priori to be the same with the one of the proposed trial, and consisted of a composite of all-cause mortality, MI, acute renal failure, coronary revascularization (either percutaneous coronary intervention or open coronary artery bypass), or stroke, within 90 days from the index operation. Mortality was defined as death from any cause and was ascertained from the Vital Status patient file. MI was defined as a serum troponin I of at least 1ng/ml that was upwards trending in patients who either a) did not have elevated troponin preoperatively, or b) did not have any preoperative troponin I check. Clinicians do not routinely order postoperative troponin; thus, we assumed that that test was requested in patients with either EKG findings or symptomatology suggestive of MI, satisfying the Third Universal Definition. Although the 99th percentile upper reference limit of troponin I is 0.06 ng/ml or less for most assays used, we employed a more conservative cutoff of 1ng/ml to minimize overestimation of the endpoint by patients who might have had mild troponin elevation from non-ischemic causes. Acute renal failure was defined as acute kidney injury (AKI) stage 3 according to RIFLE criteria (serum creatinine at least > x3 of baseline, or serum creatinine > 4 mg/dl and rise > 0.5 from baseline). The creatinine value just prior to the date of the index operation was considered as baseline for those calculations. Urine output criteria are also included in the RIFLE classification; however, urine output cannot be reliably determined from a database review, and for this reason our assessment of AKI stage 3 from this analysis may have been conservative. Coronary revascularization was ascertained using appropriate CPT codes for either percutaneous or open coronary interventions. Finally, we attempted to identify postoperative stroke using the ICD-9 code 997.5; however, this return no events. Unlike the rest of the outcomes, extracting reliable stroke rates from the CDW database is not straightforward. Furthermore, single institution data have shown the 90 day stroke rate after vascular interventions to be low (approximately 1%), which is possibly why the database query returned Transfusion Trigger after Operations in High Cardiac Risk Patients (TOP)

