Clinical Data: The site coordinator will also collect clinical data using information from the medical record and consult with the surgeon as needed. These will include height, weight, last preoperative serum Hb, albumin, blood pressure, and history of comorbidities, including coronary artery disease, end-stage renal disease, chronic obstructive pulmonary disease, hyperlipidemia, diabetes mellitus, and hypertension.

To assure that MI or acute renal failure have not occurred prior to the time of randomization the patient's chart will be reviewed for Troponin, EKG, and serum creatinine. If these values are available in the 24 hrs. prior to randomization, they will not be collected again. If unavailable within this period, EKG, serum creatinine, and troponin data will be collected within 24 hours from the time of randomization. If available at the institution, CK-MB will also be collected (not required).

We will also collect information on prior history of MI, coronary artery bypass, and stent placement. Furthermore, intraoperative assessments will be collected during the surgical procedure, such as type of operation, amount of intraoperative blood loss, intraoperative transfusion, amount and type of fluids administered, and length of the operation.

Lab, transfusion, EKG ordering procedures: Once the participant is randomized, a study team member should enter a CPRS note indicating (1) randomization arm, (2) lab/EKG collection schedule, and (3) transfusion regimen. When possible, the lab, EKG, and transfusion orders should be placed by a study team member. If verbal lab or transfusion orders are given by the

LSI to a resident or nurse, the order should be co-signed by the LSI according to the local facility's standard operating procedure. If the co-sign option is unavailable under Orders, the LSI or study team member must enter a CPRS note after the order has been placed indicating that the order was placed by resident/nurse at the LSI's request. If the note is entered by a study team member, the note must be co-signed by the LSI.

2. Follow-up Assessment

Follow-up assessments will be collected after participants are discharged from the hospital including 30- day and 90-day active follow-up assessments and one-year passive follow-up assessment.

a) Thirty Day Follow-up

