The active follow up period for study purposes will be up to 90 days after randomization. If the participant refuses to continue participation during active follow up, his or her participation in the study will be terminated. All participants who complete the active follow-up phase of the study will be followed up to one year by the Chair's Office to assess mortality using a combination of phone call follow-up, search of the DAF, or electronic medical record

assessment. If a participant declines to participate in long term follow up then one year mortality data for this participant will not be collected. Given that the one year follow up is passive and does not involve any participant action we do not anticipate this to become a major issue.

X. TRANSFUSION STRATEGIES

Participants will be randomized to a liberal (transfuse if Hb <10 gm/dl) or restrictive (transfuse if Hb <7gm/dl) transfusion groups. Transfusion will be administered in order to maintain Hb just above the aforementioned thresholds for the index hospital stay or up to 30 days after randomization, whatever comes first. A participant must be randomized within 24-hrs of the first postoperative Hb falling below 10 gm/dl. It is strongly recommended that the transfusion treatment is initiated as soon as possible after and no longer than 24 hours from identifying a protocol-required transfusion Hb threshold. Transfusions will be administered according to the following scheme.

- A. Liberal group (transfusion trigger: Hb < 10 gm/dl)
 - i. If Hb < 7.5 gm/dl transfuse three units PRBCs, then check Hb. Based on the return Hb value, follow the transfusion protocol (steps i, ii, or iii) until Hb \geq 10.
 - ii. If $7.5 \leq$ Hb < 8.5 gm/dl transfuse two units PRBCs, then check Hb. Based on the return Hb value, follow the transfusion protocol (steps i, ii, or iii) until Hb \geq 10.
 - iii. If Hb \geq 8.5 gm/dl transfuse one unit PRBCs, then check Hb. Based on the return Hb value, follow the transfusion protocol (steps i, ii, or iii) until Hb \geq 10.
- B. Restrictive group (transfusion trigger: Hb < 7 gm/dl)
 - i. If Hb < 5.5 gm/dl transfuse of two units PRBCs, then check Hb. Based on the return Hb value, follow the transfusion protocol (steps i, or ii) until Hb \geq 7.
 - ii. If $5.5 \leq$ Hb < 7 gm/dl transfuse one unit PRBCs, then check Hb. Based on the return Hb value, follow the transfusion protocol (steps i, or ii) until Hb \geq 7.

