Participant Hb, creatinine, and troponin levels will be collected on days 1, 2, 3, 4, and 7 post-randomization or discharge (whatever is shortest). EKG will be performed on days 1 and 4 after randomization. If a participant is discharged prior to post-randomization day 4, EKG will be obtained at discharge. Results on Hb (standard of care/per transfusion protocol requirements), creatinine, troponin, and EKG performed at other time points will also be collected until discharge as supporting documentation for endpoint adjudication. If available at the institution, CK-MB will also be collected (not required).

Urine output will also be monitored in patients admitted to the Intensive Care Unit and it will be reviewed daily by the Study Coordinator. If the patient has anuria for more than 12 hours, or has urine output less than 0.3 ml/Kg/hr for more than 24 hours then the urine output will be documented as evidence for the development of ARF.

Hemoglobin and transfusion record: We will record the number of blood transfusions during the preoperative, intraoperative, and postoperative time periods. The protocol requires that Hb levels be measured on day of randomization, days 1,2,3, and 4 after randomization as well as on day 7 if the participant remains in the hospital. Hb measurements, performed as standard clinical practice, will also be recorded. The Site Coordinator will record information on a) preoperative, intra-operative, and postoperative transfusions, and b) Pre- and post-randomization Hb levels. Information on Hb levels and transfusions will be obtained by contacting the hospital laboratory directly or from the chart. Information on transfusions will be obtained from the chart and the blood bank.

XI. MONITORING AND REPORTING SERIOUS ADVERSE EVENTS

A. Importance of Serious Adverse Event Reporting

Timely and complete reporting of safety information assists study management in identifying any untoward medical occurrence, thereby allowing: a) protection of safety of study participants, b) a greater understanding of the overall safety profile of the study treatments and therapeutic modalities, c) improvements in study design or procedures, and d) compliance with regulatory requirements.

B. Role of the Local Site Investigator in Serious Adverse Event Monitoring

The local site investigator, as well as other site personnel, shall be personally responsible for the following requirements:

1. Closely monitoring all study participants for new SAEs;

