these values are available in the 24 hours prior to randomization, they will not be collected again. If unavailable within this period, ECG, serum creatinine, and troponin data will be collected within 24 hours from the time of randomization.

We will also collect information on prior history of MI, coronary artery bypass, and stent placement. Furthermore, intraoperative assessments will be collected during the surgical procedure, such as type of operation, amount of intraoperative blood loss, intraoperative transfusion, amount and type of fluids administered, and length of the operation.

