5.3. Analysis Conventions

This section details general policies to be used for the statistical analyses. Departures from these general policies may be given in the specific detailed sections of this statistical analysis plan. When this situation occurs, the rules set forth in the specific section take precedence over the general policies. The following policies will be applied to all data presentations and analyses.

All statistical tests will use a significance level of $\alpha = 0.05$ unless otherwise specified. Two-tailed tests will be performed for all analyses that use statistical testing.

All p-values will be rounded to 3 decimal places. All p-values that round to 0.000 will be presented as ‘<0.001’ and p-values that round to 1.000 will be presented as ‘>0.999’. Any p-value $\leq \alpha$ will be considered statistically significant.

Summary statistics will consist of the number and percentage of responses in each category for discrete variables, and the mean, median, standard deviation (SD), minimum, and maximum for continuous variables.

All mean and median values will be formatted to one more decimal place than the measured value. Standard deviation values will be formatted to two more decimal places than the measured value.

All percentages will be rounded to one decimal place. The number and percentage of responses will be presented in the form XX (XX.X), where the percentage is in the parentheses. The decimal of the percentage may be dropped due to space constraints when creating a table.

All listings will be sorted for presentation in order of intervention group, site number, subject number, and date of procedure or event.

All analysis and summary tables will have the population sample size for each intervention group in the column heading.

Calculating change from baseline to a visit will be done as follows: change = visit – baseline.

Unless otherwise specified, baseline is defined as the last data point before the participant is randomized.

Version 9.4 of SAS® or higher will be the statistical software package used to produce all summaries, listings, statistical analyses, and graphs.

Updated version of MedDRA will be used for adverse event and pre-intervention coding.

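### The troponin, EKG and creatinine meant to rule out an MI before randomization may be taken up to 24 hours after it, so such an MI cannot be reliably separated from a primary-endpoint MI

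*Protocol*

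**What the plan says.** Protocol IX.C.1 (Baseline Assessment, Clinical Data) gives the purpose of the chart check for troponin, EKG and creatinine: "To assure that MI or acute renal failure have not occurred prior to the time of randomization". Values from the 24 hours before randomization are accepted. Otherwise: "If unavailable within this period, EKG, serum creatinine, and troponin data will be collected within 24 hours from the time of randomization". SAP 4.4.1 states the same purpose and the same fallback: "If unavailable within this period, ECG, serum creatinine, and troponin data will be collected within 24 hours from the time of randomization".

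Other passages bear on the timing:

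- **Post-randomization sampling.** Protocol X: "Participant Hb, creatinine, and troponin levels will be collected on days 1, 2, 3, 4, and 7 post-randomization or discharge". SAP Appendix 2 adds a Day 0 laboratory and EKG entry, but does not say that Day 0 samples must precede the randomization call.
- **Start of study treatment.** Protocol X recommends: "transfusion treatment is initiated as soon as possible after and no longer than 24 hours", counted from the hemoglobin value that calls for transfusion. It also requires randomization within 24 hours of the first postoperative hemoglobin below 10 gm/dl.
- **Time at risk before randomization.** Under Protocol VII.A the qualifying hemoglobin may occur up to 15 days after surgery. An MI in that interval is not among the exclusions in VII.B.
- **Endpoint.** Protocol V.A and XVI.E.2 count MI within 90 days of randomization, and Table 4 lists it as a post-randomization event. SAP 7.1 has a committee adjudicate every component.

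**The concern.** The fallback works against the purpose given for it. It applies only when the preceding 24 hours are empty, and it can then be met by a sample drawn after randomization. That sample may fall close to the scheduled day-1 draw, and it may follow the first transfusion given under the assigned strategy. If it shows a raised troponin, nothing in the rule guarantees an earlier value against which to judge whether the injury was already there.

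MI is a main component of the primary composite. An intraoperative or early postoperative MI that is first documented after randomization, and dated to that sample, adds an event that neither strategy could have prevented. Such events shrink the contrast between arms and cost power.

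The same fallback covers creatinine. The renal-failure endpoint, however, takes its reference value from admission before surgery, so the sampling-time problem discussed here is mainly one for MI.

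**Working it through.** **Step 1: can a fallback sample meet the stated purpose?**

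| Element | What the text requires |
|---|---|
| Purpose | Establish that no MI or renal failure occurred before randomization |
| Values accepted first | Any from the 24 h before randomization |
| Fallback | Used only if that window is empty; satisfied by a sample up to 24 h after randomization |
| Day 0 entry, SAP Appendix 2 | Same calendar day; order relative to the call not specified |
| Baseline collection period, Protocol IX.C.1 | From identification to randomization (or day 15 or discharge), but the fallback overrides this for these tests |

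A site may choose to draw the sample before the call, but nothing obliges it to. A sample drawn afterwards cannot fulfil the purpose.

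**Step 2: reproduce the planned sample size.** Inputs from Protocol XVI.B and SAP 4.5: p1 = 0.30, p2 = 0.225, two-sided 5%, 90% power, 5% dropout. With pooled variance and no continuity correction:

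n per arm = [1.95996·√(2·p̄·q̄) + 1.28155·√(p1q1 + p2q2)]² / (p1 − p2)²

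Here p̄ = 0.2625, so 2·p̄·q̄ = 0.38719, with root 0.62224. Next, p1q1 + p2q2 = 0.21 + 0.174375 = 0.384375, with root 0.61998.

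n = (1.21957 + 0.79454)² / 0.005625 = 721.2, rounded up to 722 per arm, or 1444 in total. 1444/0.95 = 1520. Both match the plan.

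**Step 3: dilution.** Let x be the share of participants whose pre-randomization MI is counted as an endpoint event, equally in both arms and in addition to the planned rates. The documents give no value for x; **1% to 5% is an assumption**.

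Restrictive = x + (1 − x)·0.30; liberal = x + (1 − x)·0.225

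Power = Φ{[(p1 − p2)·√722 − 1.95996·√(2·p̄·q̄)] / √(p1q1 + p2q2)}

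| x | Restrictive | Liberal | Difference (points) | Relative reduction | Power | Total N for 90%, before dropout |
|---|---|---|---|---|---|---|
| 0 | 30.0% | 22.5% | 7.500 | 25.0% | 90.0% | 1444 |
| 1% | 30.7% | 23.275% | 7.425 | 24.2% | 88.9% | 1500 |
| 3% | 32.1% | 24.825% | 7.275 | 22.7% | 86.6% | 1614 |
| 5% | 33.5% | 26.375% | 7.125 | 21.3% | 84.1% | 1734 |

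For x = 5%: (0.07125·26.870 − 1.95996·0.64769)/0.64573 = (1.9145 − 1.2694)/0.64573 = 0.999, and Φ(0.999) = 0.841.

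**Step 4: sensitivity to the accounting.** The planning rate in Protocol XVI.A runs from the index operation, so some of these MIs may already be inside the 30%. Holding restrictive at 30% and setting liberal to x + 0.75·(0.30 − x) gives power of 87.9%, 82.8% and 76.4% at 1%, 3% and 5%. This rests on the same unsupported x.

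**Step 5: how plausible is x?** Protocol Table 2 gives 90-day MI rates, from operation, of 11.0% (nadir 6-9 gm/dl) and 6.2% (nadir 9-10 gm/dl). An x of 5% would be 5/11.0 = 45% of the first and 5/6.2 = 81% of the second, so it is a pessimistic upper end. That database used a troponin cut-off of 1 ng/ml, so the trial's MI rate may differ.

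**The case against.** The strongest reply is that other safeguards do most of the work. Every participant's chart is reviewed. Troponin is repeated through day 7, and other results to discharge are kept to support adjudication. The adjudicating committee does not know the allocation. A troponin that only falls from the first sample onward is itself a clue to earlier onset. This stands: some MIs can be dated correctly. What remains is that none of these safeguards creates a pre-randomization value where none was taken.

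Several stronger readings are tempting but not supported:

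- **That pre- and post-randomization MIs can never be told apart.** The safeguards above contradict this. In addition, Protocol Appendix I (the MI definition) and the MI confirmation form could not be read for this review, so a dating rule there cannot be ruled out.
- **That the endpoint fails to require a post-randomization MI.** The primary definition attaches that label to death and stroke, but the 90-day window and Table 4 make the intent clear for MI too.
- **That the fallback is the usual case.** The protocol remarks that "Clinicians do not routinely order postoperative troponin", but this explains an assumption in a 2000-2014 database study. The same sentence assumes that the test was ordered when EKG or symptoms suggested MI. It does not describe practice at the trial sites.
- **That these participants have no baseline under the SAP.** SAP 5.3 says "baseline is defined as the last data point before the participant is randomized", but only as a default that yields to specific sections such as 4.4.1. The SAP's baseline table does not use troponin or EKG, so little analysis turns on it.
- **That the post-MI option to leave the assigned strategy will be used for MIs present at entry.** Protocol X limits that option to an MI after randomization; its use for earlier ones is speculation.

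**Conclusion.** The point holds as a mismatch between a stated purpose and the sampling rule, found in both documents. For participants with no troponin or EKG in the 24 hours before randomization, an MI arising between surgery and randomization cannot be reliably separated from a primary-endpoint MI.

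How many participants this affects is unknown. Under the assumed 1% to 5% counted in addition to the planned rates, power falls from 90% to 89-84%. The estimate assumes that misdating is equally common in both arms and that the planned effect applies to everyone else.

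A reader might infer that the result is biased toward one strategy. The documents do not support that: assignment is random and adjudication is blinded, so the expected effect is mainly dilution toward no difference. The change is worth making because it is cheap and concerns a main component of the primary endpoint. The design's sample-size arithmetic is correct.

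**What to change.** **Protocol IX.C.1 and SAP 4.4.1.** Replace the fallback with: if unavailable, EKG, troponin and creatinine are obtained before the randomization call; troponin and creatinine may be added on to the qualifying hemoglobin sample where possible. Place no condition on the timing of transfusion, and leave the MI definition as it is.

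**Participants already enrolled.**

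1. Flag those without a pre-randomization troponin or EKG, and report their number by arm.
2. Have the blinded committee classify each MI first evident on the first post-randomization sample as present at entry or new, under the existing definition.
3. Add to SAP 7.1 a sensitivity analysis of the primary endpoint that does not count MIs first shown on that sample. Other component events in the same participants still count. This analysis will also drop some genuine early MIs, so it should support the primary analysis and not replace it.

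**Cost.** The tests are already required; only their order changes. Expect an occasional short wait before the randomization call, within the 24 hours already allowed after the first hemoglobin below 10 gm/dl, and a few more deviations. The steps for enrolled participants need no new patient procedures, and they remain available if enrollment has ended.

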Pneumonia will be defined according to the CDC definition as chest radiograph or imaging with new or progressive infiltrate, consolidation, cavitation, or pleural effusion and any of the following: new onset of purulent sputum or change in character of sputum, or organism isolated from blood culture, trans-tracheal aspirate, bronchial brushings, or biopsy.

Sepsis will be defined as a combination of two of the following systemic inflammatory response syndrome (SIRS) criteria, **plus** suspected or present source of infection. SIRS criteria will

include the following: temperature greater than 38C, heart rate greater than 90 beats/min, WBC > 12,000 or < 4,000, or > 10% bands.

Outcome 2: A composite endpoint of cardiac complications (other than MI) at 90 days post-randomization: Cardiac complications will include new cardiac arrhythmias that necessitate new treatment, new or worsening congestive heart failure (CHF), and cardiac arrest not leading to death.

The diagnosis of cardiac arrhythmias will be based on EKG findings. Only arrhythmias that result in initiation of new treatment regimen (to include medications, implantable devices, or surgical intervention) during hospitalization will be recorded.

CHF will require at least one of the following symptoms or signs new or worsening: dyspnea at rest, orthopnea, or paroxysmal nocturnal dyspnea **and** radiological evidence of heart failure or worsening heart failure **and** increase/initiation of established treatment.

Cardiac arrest will be defined as the cessation of cardiac pump function activity that results in loss of consciousness and absence of circulating blood flow as evidenced by absent carotid pulse. Only episodes of cardiac arrest that are reversed will be collected under this endpoint. If they are not reversed the event will be categorized as death.

Outcome 3: All-cause mortality at 1 year after randomization.

We will determine vital status by telephoning participants after hospital discharge, by searching the electronic medical record and the VHA Death Ascertainment File (DAF).

Outcome 4: A composite endpoint of all-cause mortality, MI, coronary revascularization, acute renal failure, or post-randomization ischemic stroke at 30 days after randomization.

Outcome 5: Length of hospital stay.

C. Tertiary Outcomes

We will examine individual rates of the outcomes that consist of individual components of the primary endpoint.

VI. SUMMARY OF STUDY DESIGN

[figure not shown]

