reviewed in the electronic medical record to ascertain the presence of coronary revascularization, stroke, MI, or acute renal failure.

c) One Year Follow-up

This will be follow up performed by trained staff from the Chair's office who will call all study participants at twelve months after randomization to ascertain vital status. The CSPCC will generate listings of participants due for follow-up which will be sent to the Chairman's personnel responsible for conducting the telephone interviews. Follow-up data will be obtained by study staff. This removes the need for personal identifying information to be maintained at the individual sites or the CSPCC and helps to protect participant confidentiality. Furthermore, chart reviews using the CAPRI/VistaWeb/JLV system will be performed as a participant's death and the date of death are typically documented in the electronic medical record. Access to the national electronic health record will be requested. The VHA Death Ascertainment File (DAF) will be used to assess the one year vital status of those participants discharged alive from the hospital for whom vital status cannot be determined. Social Security number will be used to obtain the patient identifier PatientICN, which will be necessary for linkage to the DAF. We will request DAF data for all participants that have been randomized in the study. All additional deaths identified through the DAF will be reported by study staff to the CSPCC staff in an electronic file.

D. Missed Visits and Termination

1. Missed Visits

If the subject fails to present to the clinic for follow-up visit, the site coordinator at the site will call the participant within 10 days to inquire about the reason for the missed visit and to reschedule the participant's appointment as soon as possible. If the participant still refuses to come for a clinic visit, the site coordinator will complete as much of the assessment as possible on the phone and using information from the electronic medical records. We anticipate issues with no-show for clinic visits to be minimal, as standard of care entails that participants need to present for frequent clinic visits after the major operations included in this study. Missed visits will be documented. The Site Coordinator will maintain a phone log that will include date, time, phone number called, reason for the missed visit, rescheduled date of clinic appointment, and/or reason for visit refusal.

2. Termination

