Ninety Day Follow-up: Participants will be given a clinic appointment within two weeks (+ only) after the 90th post-randomization day. Questions regarding symptoms related to cardiac events, stroke, infectious complications will be asked as described above for the 30-day post-randomization follow up. If participants are unable to make the clinic visit within two weeks of the assigned appointment then an electronic medical record review and phone call follow-up will be performed as described above. Readmissions since previous follow-up will also be investigated with similar series of actions as with the 30-day post-randomization follow-up. Pertinent laboratory values (creatinine, troponin), EKG results, cardiac catheterization reports and operating room reports since the previous visit will be reviewed in the electronic medical record to ascertain the presence of coronary revascularization, stroke, MI, or acute renal failure.

One Year Follow-up: Follow up will be performed by trained staff from the Chair's office at twelve months after randomization to ascertain vital status. The CSPCC will generate listings of participants due for follow-up which will be sent to the Chairman's personnel responsible for conducting the telephone interviews. Follow-up data will be obtained by study staff. This removes the need for personal identifying information to be maintained at the individual sites or the CSPCC and helps to protect participant confidentiality. Study participants will be called, chart reviews will be performed, and the VHA Death Ascertainment File (DAF) data will be used to determine a participant's death and date of death. The DAF will be used to assess the one-year vital status of those participants discharged alive from the hospital for whom vital status cannot be determined. Social Security number will be used to obtain the patient identifier PatientICN, which will be necessary for linkage to the DAF. The data collection schedule as shown in Appendix 2.

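### Protocol IX.D.2 ties one-year mortality follow-up to completing the 90-day phase, while IX.C.2.c covers everyone randomised; the SAP does not say which rule holds or how unknown status is handled

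*Protocol*

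**What the plan says.** The outcome is listed in Protocol V.B: "Outcome 3: All-cause mortality at 1 year after randomization". Protocol XVI.E.1 and SAP 7 analyse secondary endpoints in the ITT population, which by definition keeps people who drop out (Protocol XVI.E.1, SAP 5.4).

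Protocol IX.D.2 (Termination) makes three statements about who is followed:

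- On early refusal: "If the participant refuses to continue participation during active follow up, his or her participation in the study will be terminated".
- On one-year follow-up by phone, DAF search or record review: "All participants who complete the active follow-up phase of the study will be followed up to one year".
- On a participant who declines long-term follow-up: "then one year mortality data for this participant will not be collected".

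Protocol IX.C.2.c (One Year Follow-up) is inclusive. It refers to Chair's office staff "who will call all study participants at twelve months after randomization to ascertain vital status", and it adds: "We will request DAF data for all participants that have been randomized in the study".

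SAP 4.4.2 repeats the one-year procedure without a completer condition. It applies the DAF to "those participants discharged alive from the hospital for whom vital status cannot be determined", and it leaves out the protocol's sentence on requesting DAF data for all randomised.

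**The concern.** For a participant who stops before day 90, the two protocol sections point in different directions. IX.D.2 ends participation and names completers as the group followed to one year, with the DAF search included in that follow-up. IX.C.2.c has everyone called and everyone's DAF data requested. Staff following one section would have no one-year status for that person; staff following the other would.

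All-cause mortality is hard to misclassify and, in this system, can be obtained without the participant doing anything. Completing 90 days of active follow-up happens after randomisation and may depend on both prognosis and arm, since treating physicians are not blinded (Protocol VI). Seeking the outcome only in completers would therefore leave avoidable gaps that may be related to death. Not every early exit is a refusal. The note to the exclusion criteria in Protocol VII.B requires termination after a positive COVID-19 test between randomisation and discharge. SAP Table 6 also lists administrative termination, relocation, loss to follow-up and serious adverse events other than death.

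**Working it through.** **1. The rules side by side**

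| Participant | Protocol IX.D.2 | Protocol IX.C.2.c | SAP 4.4.2 |
|---|---|---|---|
| Completes 90 days, accepts long-term follow-up | Followed: phone, DAF, record | Called; DAF requested | Called; chart; DAF if status undetermined |
| Refuses to continue before day 90 | Participation ended; not in the group named for one-year follow-up | Covered by the DAF request | No completer condition; early terminators not mentioned |
| Terminated early for another reason | Not mentioned; not a completer | Covered by the DAF request | Not mentioned |
| Declines long-term follow-up | Mortality data not collected | Covered by the DAF request | Not mentioned |

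The sections agree on the first row only.

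**2. What happens to an unknown status.** Protocol XVI.G and SAP 5.2 describe a search of VA databases for dropouts, but for the primary outcome only. Multiple imputation is optional, and the endpoints it applies to are not named. SAP Table 18 has rows for died, alive and total at one year and none for unknown. The analyst would have to drop such a person or count them as alive, with no rule for choosing.

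**3. The planned sample size, reproduced.** Inputs from Protocol XVI.B and SAP 4.5: 30% vs 22.5%, two-sided alpha 0.05, power 90%, dropout 5%.

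- Mean rate: (0.30 + 0.225)/2 = 0.2625.
- n per arm = [1.960 × √(2 × 0.2625 × 0.7375) + 1.282 × √(0.30 × 0.70 + 0.225 × 0.775)]² / 0.075², which rounds up to 722. The total is 1444, as stated.
- 1444/(1 − 0.05) = 1520, as stated.

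**4. How many could be affected.** 1520 − 1444 = 76, or 5% × 1520. This is the ceiling at planned dropout, reached only if every dropout lacks one-year status.

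**5. How far the result could move.** If a fraction m per arm is unknown, the best-case to worst-case range of the risk difference is 2m wide: 4 percentage points at m = 2%, 10 at 5%, 20 at 10%.

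**6. Illustration of bias.** The documents give no one-year mortality rate, so these inputs are assumed: true mortality of 20% in both arms, 3% unknown in the liberal arm and 7% in the restrictive arm. With mortality d among the unknown, the rate among those observed is (0.20 − m × d)/(1 − m).

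- d = 30%: (0.20 − 0.009)/0.97 − (0.20 − 0.021)/0.93 = 0.44 points.
- d = 50%: (0.20 − 0.015)/0.97 − (0.20 − 0.035)/0.93 = 1.33 points.
- d = 20%, or equal m in both arms: 0.

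Reversing the two missing fractions reverses the sign.

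**7. Power.** At the secondary alpha of 0.01 and an assumed 20% vs 15%, power is 0.50 with 760 per arm and 0.47 with 722.

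**The case against.** The best defence is that IX.C.2.c is the section written for this follow-up and it is inclusive. IX.D.2 says that completers will be followed; it does not say that nobody else will. Its one express bar on collection is for those who decline long-term follow-up, which it does not expect to be a major issue. SAP 4.4.2 carries no completer restriction. Missed visits are handled by phone and record review (IX.D.1) and do not lead to termination. Some who refuse may also withdraw permission for record access, and that must be respected.

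Most of this stands and limits the point. A reader might infer three stronger claims, none of which the documents support:

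- *That collection is limited to completers in so many words.* The limit is implied by ending the participation of those who refuse and naming completers as the group followed.
- *That the endpoint stops being intention to treat.* The ITT set is defined separately and keeps dropouts. What would change is that some of its members have no observed outcome.
- *That 76 participants will be lost.* The 5% is an allowance made for the 90-day primary endpoint. It is not an estimate of unknown one-year status. Deaths before termination are known, and the database search for the primary outcome should capture some later deaths up to day 90.

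The defence does not remove the conflict. For people who leave early, the two sections still give different instructions, and the SAP neither chooses between them nor says what to do with an unknown status.

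**Conclusion.** The inconsistency is real and should be corrected. If IX.D.2 is applied, Secondary Outcome 3 would be missing for a subset selected after randomisation. If IX.C.2.c is applied, the outcome is sought for everyone except those who decline. The number affected is unknown: up to 76 of 1520 at planned dropout, possibly far fewer, and more only if dropout exceeds the plan. The consequence is possible selection bias. In the illustration the bias runs from zero to about 1.3 percentage points, but it rests wholly on assumed rates and vanishes if the gaps are balanced between arms or unrelated to death. Loss of power is negligible, and the primary analysis is not touched.

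**What to change.** In Protocol IX.D.2, match IX.C.2.c: seek one-year vital status from the medical record and the DAF for every randomised participant, including those who stop or are terminated during active follow-up (the COVID-19 terminations in VII.B, for example). Except only those who withdraw permission for record access. In the sentence on declining, separate declining to be contacted from declining record linkage, so that the first does not by itself forfeit the mortality data. The consent wording should be checked for what it allows.

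In SAP 4.4.2, restore the sentence on DAF data for all randomised. In SAP 7.2, keep the ITT denominator as defined in SAP 5.4 and state how unknown one-year status is handled: the main approach, whether imputation applies, and a best-case/worst-case sensitivity analysis. Add an unknown row to Table 18.

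The cost is wording. The DAF request for all randomised is already planned, the follow-up is passive, and no sample-size figure changes. The SAP changes should be made before the SAP is finalised, which SAP 5.1 places ahead of the final analysis.
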